Regarding intervention studies to increase the records of DVA performed in Primary Care, we have that of Donahue et al. who obtained a 32.5% increase in VAD by mailing the information prior to the arranged visit with their family doctor and completing it in successive visits in a period of 3 months (24).

Wisow et al., In a quasi-experimental study of 1 year duration, promoted the anticipated will in over 65 in health centers through oral and written education (a letter prior to a control visit and a subsequent reminder visit) administered by

family doctors and used another health center as a control. The result was an increase of 7'8% of registrations with respect to <1% in the control center (25). According to another study in Primary Care (Ramsaroop, 2007), the information leaflet alone is not effective and the best would be multiple educational visits to promote the attitude change phase towards the ADs procedure (26).

Hypothesis of the study

Giving brief oral and written information to patients visited by your family doctor on a prior appointment increases the proportion of DVA records by 8%.

Providing a brief oral and written information to patients visited by their family doctor in a previous appointment increases the proportion of people interested in this right (there is no previous bibliography on this data).

People who write a DVT are usually older, white, women, have more children, have a will and have more comorbidity than those who do not.

MAIN OBJECTIVE

To evaluate the effect of brief oral and written information on the advance directive document (DVA) administered by primary care physicians, compared to usual clinical practice, on the proportion of persons interested in or performing the VAD in 3 months in the adult population (over 18 years old) who attend a Primary Care appointment.

SECONDARY OBJECTIVES

Evaluate the baseline characteristics of those who perform or are interested in VAD (whether they are in the control or intervention group).

To assess the baseline characteristics of those performing the DVA and those not within the intervention group.

Evaluate the reasons why patients finally formalize the document by open question (will be categorized if there is a limited number of responses, otherwise the reasons will be described qualitatively).

Evaluate the average time to perform the DVA from the day of the patient's recruitment.

MATERIAL AND METHODS

Design

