Accepting an alpha risk of 0.05 and a beta risk of 0.2 in a bilateral contrast, 165 individuals in the intervention group and 165 in the control group are required to detect a minimum relative risk of 7.8 (= 7.8% / 1%) taking the rate of VAD in the intervention group as 7.8% and in the control group of 1%. A rate of loss has been estimated for refusing the 10% share. The POISSON approximation has been used in the statistical calculator GRANMO, version 7.12 online (Program of Research in Inflammatory and Cardiovascular Disorders, Institut Municipal de Investigació Mèdica, Barcelona, Spain)

Although hypothetically no losses are expected, they may have been relinquished to participate for different reasons. In order to avoid a selection bias produced by the relationship of giving up with the fact of wanting to do a VAD, patients refusing to participate will be excluded and the motive, age and sex will be collected to compare if there are differences between the two groups regarding these characteristics.

Ambit

Florida Nord de l'Hospitalet de Llobregat Primary Care Center, an urban area with a population of approximately 25,000 people. Multicultural neighborhood with low socioeconomic status. The follow-up time for the intervention will be 3 months.

Information sources

Records of shared clinical history in eCAP. Patient questions about independent variables if they are not recorded.

Recruitment procedure

Consecutive recruitment: They will be consecutively obtained from different quotas (both afternoon shift and morning shift) so that the sample is representative of the study population.

Participate the quotas of the center whose doctor in charge has wanted to participate in the study. In order to avoid a selection bias and a more active doctor than another to have more patients represented in the study, a mechanism will be established whereby everyone will have the same probability of recruiting a similar number: the first 6 visits of each day for 8 days. The recruitment period will be made from 01/06/2015 to 09/30/2015, until the sample is completed. The follow-up period will be 3 months for each patient (both intervention and control).

A list of random numbers will be created and divided among the 7 consultations of the participating physicians in the study. Each day, the first 6 visits to the list will be recruited for 8 days prior appointment or until the sample is completed.

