In the case of finding a very different distribution of the independent baseline variables (1st visit) between the two groups, which would indicate an obvious selection bias despite randomization, the possibility of analyzing as a cohort study by means of propensity score techniques .

- Main objective "To assess the effect of brief oral and written information on the Advance Directives (ADs) given by primary care physicians, compared to usual clinical practice, on the proportion of persons interested in or performing VAD in 3 months in a heterogeneous group of patients (different ages and ethnicities) who go to a previous appointment ": inferential analysis of effectiveness, analysis of proportions of two samples. A multivariate logistic regression analysis with the variables of interest or realization of the yes / no VAS as the dependent variable will be performed and the group assigned as an independent variable, adjusting for the potential confounding factors.
- Secondary objectives: demographic and clinical characteristics that are considered likely to be associated with the completion of a priori VAD or that differ between study groups will be included in the logistic regression model for the dichotomous dependent variable.

1 · "Evaluate the baseline characteristics of those who perform or are interested in the VAD of both the control group and the intervention group": descriptive analysis for independent quantitative variables (age, number of children) and for qualitative variables , studies, comorbidity, religion, testament, marital status), frequency tables. Bivariate analysis using as a dependent variable the answer yes or no to the realization of the DVA or interest by DVA and as independent variables the basal characteristics. The Student's t test or the Mann-Whitney U test (according to the frequency distribution of the variables studied) will be used to compare continuous variables, and Chi-square or Fisher's exact test for comparison of categorical variables.

2 · "Evaluate the baseline characteristics of those who perform the VAD and those who are not in the intervention group": descriptive analysis for independent quantitative variables (age, number of children) and for qualitative variables (gender, race, comorbidity, religion, testament, marital status), frequency tables.

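### The bivariate tests for secondary objective 1 pool both arms without an arm term; stratifying by randomised arm would recover some power and remove the effect of chance arm imbalance, a minor improvement

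*Protocol*

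**What the plan says.** Under Secondary Objectives, the Protocol sets out to "Evaluate the baseline characteristics of those who perform or are interested in VAD (whether they are in the control or intervention group"). The statistical section of the Protocol and the separate SAP implement this in the same words, as item 1 of the secondary analyses: "Bivariate analysis using as a dependent variable the answer yes or no to the realization of the DVA or interest by DVA", with the baseline characteristics as the independent variables. The tests are Student's t or Mann-Whitney for continuous characteristics and chi-square or Fisher for categorical ones. Arm is not mentioned in item 1, either as a term or as a stratum, and no effect estimate is named.

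Two neighbouring passages matter.

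- The paragraph that opens the secondary objectives sends some characteristics into a logistic model: those thought in advance to be linked to completion, and those that differ between the arms. The only logistic model described, under the main objective, has the assigned group as a term.
- Item 2 repeats the predictor comparison inside the intervention arm, but for completion of an advance directive (AD) only, not for interest.

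**The concern.** The trial is built on the expectation that arm strongly affects this outcome. Under the Protocol's Intervention section, only intervention patients are told about ADs and invited to come back for more. A control patient who asks for the information is excluded as a refusal, although interest is still asked about in both arms at follow-up. Most patients with a yes answer should therefore come from the intervention arm.

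Leaving a strong determinant of the outcome out of a predictor analysis has two consequences. Variation between arms stays in the error, which costs power. And if a characteristic happens to differ between the arms, part of the arm effect shows up as an apparent association with that characteristic. At stake is the reliability of the list of predictors that objective 1 will yield.

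**Working it through.** **The plan's own figure.** The Protocol's sample-size section works with a two-sided 5% level, 80% power and completion of 7.8% against 1%. Its result is that "165 individuals in the intervention group and 165 in the control group are required", after an allowance of 10% for loss. On the method it says: "The POISSON approximation has been used in the statistical calculator GRANMO". With Poisson variance:

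n = (1.960 + 0.842)² × (0.078 + 0.01) / (0.078 − 0.01)² = 7.849 × 0.088 / 0.004624 = 149.4 per arm.

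For 10% loss, 149.4/0.9 = 166.0 and 149.4 × 1.1 = 164.3, which rounds up to 165. The figure of 165 is reproduced. These rates concern completion only.

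**Inputs for the check.**
- 148 per arm (165 × 0.9 = 148.5, rounded down).
- Completion 7.8% vs 1%, from the sample-size section.
- Interest rates: assumed. The Protocol's hypothesis section says there are no earlier data. I use 15% vs 1%, 25% vs 2% and 39% vs 2%. The 39% is the share in a primary care survey cited in the Protocol who said they would make an AD, so it is an upper illustration.
- Characteristic present in 50% of patients, with an odds ratio of 2 within each arm: assumed. The Protocol's background gives women as about twice as likely to complete.

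**Case mix.** At 25% vs 2%, 0.25/(0.25 + 0.02) = 93% of yes answers come from the intervention arm, and 0.98/(0.98 + 0.75) = 57% of no answers from control. At 7.8% vs 1%, the figures are 0.078/0.088 = 89% and 0.99/(0.99 + 0.922) = 52%.

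**Information lost by pooling.** With p̄ the mean of the two arm rates, the variance ratio is p̄(1 − p̄) divided by the mean of p(1 − p) over arms.
- 7.8% vs 1%: 0.0421/0.0409 = 1.03
- 25% vs 2%: 0.1168/0.1036 = 1.13
- 39% vs 2%: 0.1630/0.1288 = 1.27

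**Pooled odds ratio when it is 2 in each arm.** At 25% vs 2%, the risks without and with the characteristic are 18.6% and 31.4% (intervention) and 1.35% and 2.65% (control). They average 9.98% and 17.02%, so the pooled odds ratio is (0.1702/0.8298)/(0.0998/0.9002) = 1.85. The same steps give 1.73 at 39% vs 2% and 1.96 at 7.8% vs 1%.

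**Simulation.** Pooled chi-square against Mantel-Haenszel stratified by arm, two-sided 5%, 148 per arm, at least 40,000 trials per scenario:

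| Rates (intervention vs control) | Power for OR 2, crude | Power for OR 2, stratified |
|---|---|---|
| 7.8% vs 1% (documented, completion) | 20.6% | 21.0% |
| 15% vs 1% (assumed) | 31% | 33% |
| 25% vs 2% (assumed) | 42–43% | 47% |
| 39% vs 2% (assumed) | 47% | 56% |

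**False positives with no true association.** In a separate run with 165 per arm, overall error of the crude test was 4.7% to 5.1% across rates from 7.8% vs 1% to 39% vs 5%. Given an arm imbalance of |z|>1.5 (about a 13% chance for any one characteristic) and 148 per arm, it is about 8.4% at 25% vs 2% and 11.7% at 39% vs 2%, against about 5% stratified. At 7.8% vs 1% with 165 per arm, even given an imbalance significant at 5%, it is only 5.6%.

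**The case against.** The case against making anything of this is substantial.

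- **The plan does not ignore arm.** A reader of item 1 alone might infer that it does. The logistic model named under the secondary objectives takes in characteristics that differ between arms, which are the ones most exposed to the imbalance problem, and the only such model described contains the group. This largely stands. What it leaves open is that the model covers selected characteristics only, and nothing says that objective 1 will be reported from it. Item 1 specifies its own crude tests.
- **There is no systematic bias.** A reader might infer from the case mix that the comparison is mostly intervention against control, or that false positives are inflated. Patients are individually randomised, so arm is unrelated to baseline characteristics in expectation, and overall error stays near 5%. The 8% to 12% applies only given a sizeable imbalance and under assumed interest rates. At 25% vs 2%, 43% of the no group are still intervention patients.
- **The smaller pooled odds ratio is not an error.** With randomised arm, the gap between 1.85 and 2 is non-collapsibility: two different valid quantities. Item 1 promises no odds ratio in any case. This stands.
- **The gain rests on assumed rates.** At the only documented rates it is 0.4 percentage points. This stands for completion, but objective 1 also counts interest, which the intervention is meant to raise.
- **Stratifying has a cost with sparse data.** At 1% completion, 165 × 0.01 = 1.65 control completers are expected, and the chance of none is 0.99^165 = 19%. An empty control stratum adds nothing to Mantel-Haenszel, and the arm coefficient in ordinary logistic regression then has no finite estimate. This stands and is met in the fix.

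**Conclusion.** The point holds as a minor improvement to a secondary analysis. The crude tests in item 1 are valid overall, but they are less efficient than they need be and exposed to chance arm imbalance if interest is much commoner in the intervention arm. At assumed interest of 25% vs 2% to 39% vs 2%, stratifying adds roughly 4 to 9 percentage points of power for an odds ratio of 2 and brings the false-positive rate under imbalance back to about 5%. For completion alone it changes almost nothing. There the larger limit is the number of events, about 12.9 + 1.65 = 14.5 completers at the planned rates, which stratifying cannot mend.

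These sizes depend on the assumed interest rates, a characteristic present in half the patients and a common within-arm odds ratio. The statement that overall error is about 5% also assumes that exclusions after allocation (refusals, and controls who ask for information) do not themselves unbalance the arms; the documents give no figures on that. The main comparison is not affected.

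**What to change.** In item 1 of the secondary analyses, in both Protocol and SAP:

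1. Replace the crude bivariate tests by tests stratified by randomised arm: Mantel-Haenszel for categorical characteristics, or logistic regression with arm plus one characteristic at a time for all of them.
2. Report the arm-adjusted odds ratio with its 95% CI for each characteristic, and show the descriptive tables separately by arm.
3. Where control events are few or zero, use an exact stratified test or restrict the analysis to the intervention arm, and say so.
4. State whether the logistic model mentioned under the secondary objectives is meant to answer objective 1.

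The cost is a few sentences. Arm is already recorded, and no extra data or patients are needed. The small downside is that the control stratum adds little information when it holds few events, so sparse outcomes need the fallback in step 3.

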EFFECTIVENESS OF A BRIEF INFORMATION ABOUT ADVANCE DIRECTIVES IN PRIMARY CARE: A RANDOMIZED CLINICAL TRIAL

Document Date: September 14, 2017

Statistical Analysis Plan (SAP)

Intention-to-treat analysis. No intermediate analysis is planned. A bilateral significance level of 5%, 95% CI and 80% power will be used. The SPSS V21 program will be used. Analysis of efficacy of unadjusted parallel clinical trials. Data will be analyzed according to the CONSORT guidance and comparisons between groups will be based on the intention-to-treat principle. First: analysis of the baseline comparability of the study groups in relation to the variables studied. Descriptive statistics of all variables collected. The Student's t test or the Mann-Whitney U test (according to the frequency distribution of the variables studied) will be used to compare continuous variables, and Chi-square or Fisher's exact test for comparison of categorical variables.

In the case of finding a very different distribution of the independent baseline variables (1st visit) between the two groups, which would indicate an obvious selection bias despite randomization, the possibility of analyzing as a cohort study by means of propensity score techniques .

- Main objective "To assess the effect of brief oral and written information on the Advance Directives (ADs) given by primary care physicians, compared to usual clinical practice, on the proportion of persons interested in or performing VAD in 3 months in a heterogeneous group of patients (different ages and ethnicities) who go to a previous appointment ": inferential analysis of effectiveness, analysis of proportions of two samples. A multivariate logistic regression analysis with the variables of interest or realization of the yes / no VAS as the dependent variable will be performed and the group assigned as an independent variable, adjusting for the potential confounding factors.
- Secondary objectives: demographic and clinical characteristics that are considered likely to be associated with the completion of a priori VAD or that differ between study groups will be included in the logistic regression model for the dichotomous dependent variable.

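### Excluding refusers after allocation can create the selection bias it is meant to avoid, and comparing about 16 refusers per arm on motive, age and sex cannot show how much it matters

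*Protocol*

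**What the plan says.** The protocol's Calculation of sample size section names the threat and its remedy together. "In order to avoid a selection bias produced by the relationship of giving up with the fact of wanting to do a VAD", it says, "patients refusing to participate will be excluded and the motive, age and sex will be collected to compare if there are differences between the two" study groups. The same section sets the allowance, "A rate of loss has been estimated for refusing the 10% share", and then says "Although hypothetically no losses are expected".

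Four other places bear on the point:

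- **Recruitment procedure (protocol):** the physician asks for the allocation number before the patient comes in.
- **Sample (protocol):** the trial is open-label, and unwillingness to take part is an exclusion criterion.
- **Intervention (protocol):** a control patient who wants the AD information is removed and classed as having refused. The number of any patient with an exclusion criterion is not reused.
- **SAP (and the same text in the protocol):** intention-to-treat, a baseline comparison of the arms, logistic regression adjusted for confounders, and a possible propensity-score analysis if the arms differ greatly. Its general tools are tests: "The Student's t test or the Mann-Whitney U test (according to the frequency distribution of the variables studied) will be used to compare continuous variables", with chi-square or Fisher for categories. Refusers are not mentioned.

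**The concern.** The protocol fears that people who refuse may differ in how much they want an AD. Excluding them cannot prevent that bias when refusal follows allocation; it removes people from arms that randomization had made comparable. The control-only ground for exclusion points in one direction, because it takes AD-interested patients out of the control arm and so favours the intervention.

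The comparison of motive, age and sex is the only planned look at the refusers themselves. It has few patients, and two of its three variables are poor proxies for the trait that matters. No test, threshold or action is attached to it, and nothing in either document bounds what the excluded patients could do to the result. At the planned rates AD completion rests on about 12 events against 1 or 2, so a handful of patients can matter.

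**Working it through.** **1. The plan's own sample size.** Inputs, all from Calculation of sample size: "Accepting an alpha risk of 0.05 and a beta risk of 0.2 in a bilateral contrast"; "taking the rate of VAD in the intervention group as 7.8% and in the control group of 1" per cent; Poisson approximation; 10% refusal.

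- n = (1.960 + 0.842)² × (0.078 + 0.01) / (0.078 − 0.01)² = 7.849 × 0.088 / 0.004624 = 149.4 per arm.
- 149.4 / 0.9 = 166, against the stated "165 individuals in the intervention group and 165 in the control group are required". This reproduces within rounding.
- Expected refusers: 165 − 149 = 16 per arm (10% of 165 is 16.5), assuming an even split. The plan does not divide the 10% by arm.

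**2. What the comparison can detect (two-sided 5%).** The effect sizes are assumptions; the documents give none.

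| Comparison | Assumed difference | Power |
|---|---|---|
| 16 vs 16, age, t-test | 0.5 SD | 27.8% (72% missed) |
| 16 vs 16, sex | 40% vs 60% women | 21% chi-square, 12% Fisher |
| 33 vs 297, age, t-test | 0.5 SD | 78% |

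With 15 to 18 refusers per arm the age miss rate runs from 74% to 69%. Sixteen per arm reaches 80% power only at about 1.02 SD; a 0.5-SD difference would need about 64 per arm. The last row applies if the two groups are read as refusers and participants (2 × 16.5 = 33; 330 − 33 = 297), but that does not compare the arms.

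For motive, 3/16 vs 0/16 AD-related gives Fisher p=0.23 and 4/16 vs 0/16 gives p=0.10. A test could miss the pattern; a plain listing of motives would show it.

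**3. Whether the baseline comparison would pick it up.** A 0.5-SD difference between the two sets of refusers shifts the analysed arms by about 0.5 × 16.5 / 148.5 = 0.056 SD, detected about 8% of the time.

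**4. Leverage on AD completion.** Planned events are 0.078 × 149 = 11.6 and 0.01 × 149 = 1.5. Take 12/149 vs 2/149: chi-square (uncorrected) p=0.006, Fisher p=0.011. Restore 165 per arm, count no intervention refusers as events, and count k control refusers as events:

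| k | Table | Chi-square p | Fisher p |
|---|---|---|---|
| 0 | 12/165 vs 2/165 | 0.006 | 0.011 |
| 1 | 12/165 vs 3/165 | 0.017 | 0.031 |
| 2 | 12/165 vs 4/165 | 0.040 | 0.070 |
| 3 | 12/165 vs 5/165 | 0.081 | 0.133 |

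Significance is lost at k=3 by chi-square and k=2 by Fisher. Starting from 12 vs 1, one more is needed in each case.

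**5. How demanding that scenario is.** Three of 16 is 19% of control refusers, and 5/165 is 3.0% overall, against the planned 1%. If refusers were a random sample of patients, three or more AD makers among 16 would have probability 0.0005 at a 1% rate and 0.04 at 5%.

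**6. False positives with no true effect.** 165 per arm, the same AD rate in both arms, up to four would-be AD makers removed from control only, exact enumeration:

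| Rate in both arms | Chi-square | Fisher |
|---|---|---|
| 1% | 8% | under 1% |
| 2% | 33% | 9% |
| 5% | 24% | 18% |
| 7.8% | 16% | 13% |

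At 1% only 0.01 × 165 = 1.65 control completers are expected, so there are seldom four to remove. The rates and the number removed are assumptions.

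**The case against.** The strongest reply has four parts.

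- **No decision rule is written.** A reader might infer that a null comparison would be used to declare the trial free of selection bias. The protocol says only that the characteristics will be compared, and the SAP does not assign its tests to refusers. This stands. What remains is that the comparison is presented as serving to avoid the bias, which it cannot do.
- **Motive is collected.** It addresses the threat directly, and AD-related refusals in the control arm would be visible without any test. This stands, and the fix uses it. Motive shows that selective refusal occurred; the plan has no step that turns this into an effect on the result.
- **The leverage is shown on AD completion, whereas the main objective is interest in or completion of an AD.** This stands. The composite has at least as many events, in unknown number. With assumed counts of 45/149 vs 15/149, four further events among control refusers give 45/165 vs 19/165, p=0.0003. On the other hand, control patients removed because they want the information have already shown interest, so more events may need restoring for that outcome.
- **There are other safeguards.** A reader might take the refuser comparison as the trial's only protection. It is not: the plan also has intention-to-treat, the baseline comparison, adjustment and a propensity-score fallback. They do little here. The exclusion contradicts intention-to-treat, the baseline comparison is nearly blind to the shift (step 3), and adjustment uses covariates of retained patients, which cannot recover an excluded patient's wish for an AD.

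It can also be said that the control-only exclusion is the root problem. It is the clearest source of a one-directional loss, but removing it would leave ordinary post-allocation refusals still unassessed.

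**Conclusion.** The point holds in this form: excluding refusers after allocation can introduce the bias the protocol wants to avoid, the planned comparison is too small and mostly too indirect to assess it, and nothing else in the plan does so. The 28% power figure rests on the planned 10% refusal split evenly and on an assumed 0.5-SD difference in age.

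AD completion can be fragile, with significance lost when two (Fisher) or three (chi-square) control refusers count as events from 12 vs 2. This requires strong selection or a true control rate above the planned 1%. A reader might infer that three or four control refusers would generally produce a false positive. The figures do not support that: the false-positive rate is about 8% by chi-square at the planned control rate and reaches 16% to 33% only at assumed rates of 2% to 7.8%. For the composite outcome the size cannot be stated, because the protocol gives no prior data on interest.

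This is a gap to close in the analysis plan. It does not show that the trial's result would be wrong.

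**What to change.** In Calculation of sample size and in the SAP:

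1. Keep refusers' age and sex as description only, and do not present the comparison as avoiding or excluding selection bias.
2. Report refusals in each arm out of all allocated patients who meet the other eligibility criteria, with the risk difference and 95% CI. Do this overall and for AD-related motives, including control patients excluded for wanting the information.
3. Add a tipping-point sensitivity analysis for both the composite main outcome and AD completion. Restore refusers to their allocated arm, count 0, 1, 2, ... control refusers as events and no intervention refusers, and report the number at which significance is lost, naming the test.
4. Set that number beside the count of control refusers with an AD-related motive, including those excluded for wanting the information. Describe the result as robust to selective refusal only if the tipping number is larger.

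The cost is a few sentences in the SAP and one small table. It uses allocation numbers and motives that the plan already records, and needs no more patients and no access to refusers' records. The drawback is that a positive result may have to be reported as fragile.
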